16.2.2 Pharmacokinetic Parameters

PK parameters for balovaptan, M2, and M3 and will be estimated using non-compartmental methods with WinNonlin®.

The plasma PK parameters will be estimated from the concentration-time profiles. In estimating the PK parameters, BQL values will be set to zero for the pre-dose PK sample, as well as for all other samples being BLQ and occurring before T_{max} . For subsequent time points, the result will be set to missing. Actual sampling times, rather than scheduled sampling times, will be used in all computations involving sampling

times. If the actual time or dose time is missing, the scheduled time may be substituted in order to calculate the PK parameter.

Descriptive statistics (number of subjects, arithmetic mean, SD, (arithmetic) CV%, median, min, max, geometric mean and geometric CV%) will be used to summarize the calculated PK parameters by treatment. For T_{max} , only median, min and max will be presented.

16.2.2.1 Drug-Drug Interaction

The effect of itraconazole on the PK of balovaptan on Analysis Days 10 and 15 will be assessed. A linear mixed effect model will be used to analyze the natural log-transformed C_{max} and AUC_{0-tau} values of balovaptan, M2 and M3. An analysis variable representing the combination of treatment and analysis day (balovaptan alone on Day 10, balovaptan + itraconazole on Day 10, and balovaptan + itraconazole on Day 15) will be used as fixed effect and subject will be used as a random effect. The estimates for the differences between

- 1) balovaptan + itraconazole on Day 15 (test) and balovaptan alone on Day 10 (reference)
- 2) balovaptan + itraconazole on Day 10 (test) and balovaptan alone on Day 10 (reference)

will be back-transformed to derive the geometric mean ratios of balovaptan + itraconazole (on Days 10 and 15) over balovaptan alone on Day 10 together with the corresponding 90% CIs for the comparisons of the PK parameters.

In addition, as an exploratory analysis, the CYP3A4 genotype will be added as a factor. The relationship between other genotypes may also be explored.

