## **6.7 OTHER ANALYSES**

### **6.7.1 Genotyping**

The relationship between CYP3A4 genotype and steady state balovaptan exposure and the influence of CYP3A4 genotype on the effect of itraconazole on balovaptan PK and CYP3A enzyme activity will be evaluated. Other isoforms may also be analysed.

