5.3 Tertiary/Exploratory Objectives

- Relationship between the CYP3A4 genotype, among others, and steady state balovaptan exposure, and the influence of the CYP3A4 genotype, among others, on the effect of itraconazole on balovaptan PK
- The plasma exposure of itraconazole and hydroxy (OH)-itraconazole

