7.0 Overview of Planned Analysis

7.1 Changes from Protocol

There are no changes from the protocol.

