9.4.2 Predetermined Covariates and Prognostic Factors

CYP3A4 genotype will be investigated as a factor in this study, see also [Section 16.2.2.1](#).

The pharmacogenetics of other isoforms, metabolizing enzymes, transferases, transporters, etc, possibly involved in the absorption, distribution, metabolism and excretion of balovaptan and its major metabolites (e.g., CYP3A4 and P-glycoprotein) may be investigated additionally.

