9.4.3 Hypothesis Testing

No formal hypothesis testing will be done.

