9.5 TFL Layout

Report layout will be according to the PRA EDS – ICH E3 compliant – CSR Template. The layout of TFLs will be according to the PRA EDS standards.

No table shells will be provided. The TFLs will be provided in Adobe PDF format.

Format:

- Page size: A4
- Data in listings will be sorted by subject number and time point.
- Data in tables will be sorted by treatment and time point.
- Column titles will be in title case letters.
- All tables and listings will be in landscape format.
- The treatment labels will be as outlined in Section 9.2.2 Treatment/Subject Grouping Definition

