Appendix 4: List of End of Text Outputs

List of End of Text Tables and Figures:		
Output	Title	Population Set
Section 14.1 Disposition and Demographic Data		
Table 14.1.1	Summary of Subject Disposition	Safety
Table 14.1.2.1	Summary of Demographics	Safety
Table 14.1.2.2	Summary of Demographics (if applicable)	PK
Section 14.2 Pharmacokinetic Data		
Table 14.2.1	Individual Values and Descriptive Statistics of Balovaptan Plasma Concentrations by Treatment, Analysis Day and Time-Point	PK
Table 14.2.2	Individual Values and Descriptive Statistics of Balovaptan Plasma Parameters by Treatment and Analysis Day	PK
Table 14.2.3	Individual Values and Descriptive Statistics of Balovaptan Metabolite (M2 and M3) Plasma Concentrations by Treatment, Analysis Day and Time-Point	PK
Table 14.2.4	Individual Values and Descriptive Statistics of Balovaptan Metabolite (M2 and M3) Plasma Parameters by Treatment and Analysis Day	PK
Table 14.2.5	Individual Values and Descriptive Statistics of Itraconazole and OH-Itraconazole Plasma Concentrations by Treatment, Analysis Day and Time-Point	PK
Table 14.2.7	Statistical Analysis of the effect of Itraconazole on Balovaptan	PK
Table 14.2.8	Statistical Analysis of the effect of Itraconazole on Balovaptan Metabolites (M2 and M3)	PK
Figure 14.2.10	Geometric Mean Balovaptan Plasma Concentrations versus Time by Treatment and Analysis Day (Linear and Semi-Logarithmic Scale)	PK
Figure 14.2.11	Geometric Mean Balovaptan Metabolite (M2 and M3) Plasma Concentrations versus Time by Treatment and Analysis Day (Linear and Semi-Logarithmic Scale)	PK
Figure 14.2.12	Geometric Mean Itraconazole and OH-Itraconazole Plasma Concentrations versus Time by Treatment and Analysis Day (Linear and Semi-Logarithmic Scale)	PK
Figure 14.2.13	Combined Individual Balovaptan Plasma Concentrations versus Time by Treatment and Analysis Day (Linear and Semi-Logarithmic Scale)	PK
Figure 14.2.14	Combined Individual Balovaptan Metabolite (M2, M3) Plasma Concentrations versus Time by Treatment and Analysis Day (Linear and Semi-Logarithmic Scale)	PK
Figure 14.2.15	Combined Individual Itraconazole and OH-Itraconazole Plasma	PK

	Concentrations versus Time by Treatment and Analysis Day (Linear and Semi-Logarithmic Scale)	
Figure 14.2.16	Individual Balovaptan Plasma Concentrations versus Time in Days by Treatment (Linear and Semi-Logarithmic Scale)	Safety

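### The SAP's genotype model names no genotype-by-treatment/day term, so on its ordinary reading it cannot estimate whether CYP3A4 genotype changes the itraconazole effect

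*SAP*

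**What the plan says.** SAP 5.3 gives two exploratory genotype aims. The first relates CYP3A4 genotype to steady-state balovaptan exposure. The second concerns "the influence of the CYP3A4 genotype, among others, on the effect of itraconazole on balovaptan PK". Protocol 6.7.1 says that both will be evaluated, and words the second as "the influence of CYP3A4 genotype on the effect of itraconazole on balovaptan PK". SAP 7.1 adds: "There are no changes from the protocol".

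The model is in SAP 16.2.2.1. Log-transformed Cmax and AUC over the dosing interval are analysed with one three-level fixed effect (balovaptan alone on Day 10, the combination on analysis Day 10, the combination on analysis Day 15) and a random subject effect. The genotype analysis is a single sentence: "as an exploratory analysis, the CYP3A4 genotype will be added as a factor". SAP 9.4.2 says "CYP3A4 genotype will be investigated as a factor in this study" and refers back to that section. Neither document mentions a genotype-by-treatment/day term, a ratio within genotype, or individual ratios grouped by genotype.

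In SAP Appendix 4 the drug-interaction tables are 14.2.7, "Statistical Analysis of the effect of Itraconazole on Balovaptan", and its counterpart for the metabolites. Neither title refers to genotype. Genotype appears in two listings (demographics and genotyping results).

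**The concern.** The second aim is a question of effect modification: does the test/reference ratio differ between genotypes? A model with genotype only as a main effect assumes that it does not. It would therefore return a result labelled as the genotype analysis while leaving that aim unanswered.

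The main-effect coefficient is also open to misreading. It averages over balovaptan alone and two itraconazole conditions, so it mixes a genotype difference in exposure with a genotype difference in the itraconazole effect. If the model is settled only after the data are seen, the grouping and the method become data-dependent choices.

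**Working it through.** **Inputs.** Within-subject CV 39%, 12 completers, 90% CI and the stated precision factor of 1.30 come from protocol 6.1 and SAP 6.1. The documents give no genotype groups or frequencies, so the two-group splits and genotype-specific ratios below are assumptions.

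**1. The plan's own figure.** Within-subject log SD = sqrt(ln(1 + 0.39²)) = 0.3763. SE of the log ratio = 0.3763 × sqrt(2/12) = 0.1536.
- Three-level SAP model: residual df = 36 − 12 − 2 = 22, and exp(t × SE) = 1.302.
- Two-level protocol model: df = 24 − 12 − 1 = 11, and the factor is 1.318.

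The stated 1.30 is reproduced with 22 df.

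**2. Why a main effect cannot answer the second aim.** A genotype main effect shifts a subject's three log means by the same amount, so it drops out of every within-subject difference. REML mixed models were fitted to simulated complete data with a true interaction:
- 4/8 split: the Day 15 log contrast was 1.15504 (SE 0.1704), both without genotype and with the main effect.
- 6/6 split: the ratio was 2.715 in both models. The interaction model gave 3.63 and 2.03 for the two groups (true values 4 and 2).

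**3. What the main-effect coefficient measures.** Let A be the genotype ratio of exposure on balovaptan alone, and RoR the ratio of the two genotype-specific itraconazole ratios, taken as equal on both combination days. With complete data the coefficient is the average over three conditions:

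log(A) + (2/3) × log(RoR)

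- A = 1 and RoR = 0.5 gives 0.5^(2/3) = 0.63.
- A = 0.63 and RoR = 1 also gives 0.63.

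The two situations cannot be told apart.

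**4. Worked example.** Assume true ratios of 4.0 in 8 subjects and 2.0 in 4, with A = 1. The common ratio is (4⁸ × 2⁴)^(1/12) = 3.17. In 300 simulated complete data sets the averages were 3.18 for the common ratio, 0.64 for the main effect and 0.48 for the interaction contrast (true value 0.50).

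**5. Precision once the interaction is named.** SE of log RoR = 0.3763 × sqrt(2) × sqrt(1/n1 + 1/n0). The interaction uses 2 more df in the three-level model (20 left) and 1 more in the two-level model (10 left). The 20-df figures assume a common residual variance across the three conditions.

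| Assumed split | SE | 90% CI factor, 20 df | 90% CI factor, 10 df | CI excludes 1 if estimate is below (20 df) |
|---|---|---|---|---|
| 6/6 | 0.307 | 1.70 | 1.75 | 0.59 |
| 4/8 | 0.326 | 1.75 | 1.81 | 0.57 |
| 3/9 | 0.355 | 1.84 | 1.90 | 0.54 |
| 2/10 | 0.412 | 2.04 | 2.11 | 0.49 |
| 1/11 | 0.556 | 2.61 | 2.74 | 0.38 |

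The CI also excludes 1 above the inverse of the last column. At 2/10 the interval spans 2.036² = 4.1-fold.

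Genotype-specific ratios have factors exp(t × 0.3763 × sqrt(2/n)) with 20 df, smaller group first: 1.45 and 1.45 at 6/6, 1.58 and 1.38 at 4/8, 1.91 and 1.34 at 2/10.

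**The case against.** The strongest reply is that the sentence is brief rather than wrong. It does not restrict genotype to a main effect, it sits in the drug-drug interaction section, and a statistician who also reads SAP 5.3 could fit the interaction without departing from the plan. That is fair: the defect holds on the ordinary reading, not on every reading. But the sentence still supplies no estimator for the aim, and someone who follows it literally will not produce one.

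Other points carry some weight:
- SAP 5.3.1 allows pooling of pharmacogenetic results with other balovaptan studies. This lowers what depends on this study, but pooling is optional and the pooled results stay out of this study's report.
- SAP 3.0 allows changes to planned analyses to be reported in the study report without an updated SAP. That softens the need for a formal amendment, not the need to choose the model before seeing the data.
- The silence of Appendix 4 is only supporting evidence, since SAP 9.5 states "No table shells will be provided" and statistical appendices are planned where model output could go.
- Individual PK parameters (Tables 14.2.2 and 14.2.4) and genotypes (Listing 16.2.4.7) will be available, so ratios by genotype could be worked out by hand. No planned output is described as doing so.
- The first aim is not worded as exposure on balovaptan alone. An average over conditions is a legitimate answer to it when genotype does not modify the itraconazole effect, which is exactly what the second aim asks.
- With 12 completers the interaction will be imprecise. That is a reason to report it descriptively, not to leave it out.

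**Conclusion.** The concern holds. On the ordinary reading, the planned genotype model gives no estimate for a stated exploratory aim, and its coefficient confounds that aim with the other one. The cancellation is exact for complete data and does not depend on the assumed genotype splits. The sizes shown (0.63, 3.17 and the CI factors) do depend on them, and on CV 39% with 12 completers.

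The consequence is limited. The aim is tertiary, the primary geometric mean ratios and the sample size do not change, and even the right model will detect only large differences: at a 6/6 split the estimated ratio of ratios must be below 0.59, or above its inverse, for the 90% CI to exclude 1. This is a cheap improvement that should be made, not a threat to the main result.

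**What to change.** Amend the sentence in SAP 16.2.2.1 so that the exploratory model includes CYP3A4 genotype and its interaction with the three-level treatment/day variable. Keep the primary model without genotype.

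From the exploratory model, report with 90% CIs:
- the genotype-specific geometric mean ratios for Day 15 and Day 10 against balovaptan alone;
- the ratio of those ratios between genotypes;
- the genotype contrast on balovaptan alone, which addresses the first aim without mixing in the itraconazole conditions.

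Label these descriptive, in keeping with SAP 9.4.3 ("No formal hypothesis testing will be done"). Define the genotype groups before the data are seen. Where a group is too small to model (a suggested cut-off, not taken from the documents, is fewer than 3 subjects), list individual test/reference ratios by genotype instead. If only one genotype group is observed, say that the aim cannot be assessed. Name the output in Appendix 4.

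The cost is one amended sentence, one model term and one output, all from data already being collected. The drawback is wide intervals, which the report should state.

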17.0 Safety Analyses

17.1 Safety Variables

The following safety variables will be summarized:

- Adverse Events (AEs)
- Vital Signs
 - Supine Blood Pressure
 - Systolic Blood Pressure (SBP)
 - Diastolic Blood Pressure (DBP)
 - Pulse rate
 - Body temperature (tympanic)
 - Respiratory rate
- Electrocardiograms (ECG)
 - Heart Rate
 - PR Interval
 - QRS-Duration
 - QT Interval
 - QTc (Fridericia) Interval
- Clinical Laboratory Evaluations
 - Serum Chemistry
 - Hematology
 - Urinalysis
 - Coagulation
- Columbia-Suicide Severity Rating Scale (C-SSRS)
 - Suicidal ideation
 - Suicidal behavior

17.1.1 Adverse Events

All AEs will be coded to the current version of Medical Dictionary for Regulatory Activities (MedDRA, the latest version) by F. Hoffmann-La Roche, Ltd.

All AE summaries will include only treatment emergent adverse events (TEAEs). Treatment-emergent adverse events are those which occur after the first dose of study drug. AEs starting prior to medication dosing in the first period will be regarded as pre-dose AEs (i.e. non-TEAEs).

TEAEs occurring following dosing in a specific analysis period but before dosing in the next analysis period will be attributed to that specific analysis period, thus to the last treatment received. If the time is missing for an AE on a dosing day then the AE will be attributed to the treatment given on that day.

All adverse events (including non-TEAEs) recorded on the eCRF will be listed. Pre-dose AEs will be presented in a separate listing. In addition, a separate listing of AEs leading to withdrawal from study will be provided.

TEAEs will be tabulated by system organ class and preferred term: one table with all TEAEs (number and percentage of subjects) overall and by treatment; one table with related TEAEs (number and percentage of subjects) by treatment; one table with all TEAEs (number and percentage of subjects) by treatment and relationship to study drug; one table with TEAEs (number and percentage of subjects) by treatment and severity.

Subjects are counted once, per preferred term per treatment, for the most severe of multiple occurrences (in case of severity) or most drug-related event (in case of relationship) of a specific MedDRA term. AEs whose causal relationship was characterized as 'Yes'/'No' will be regarded as being related/not related to the study medication.

The following missing data will be imputed as defined (for calculations only / will not be presented):

- Missing AE start and / or end times for the calculation of onset and duration will be assumed to be at 00:01 for a start time and 23:59 for end times
- Missing AE severity or relationship will be assumed to be severe or related, respectively
- Missing AE start times for the determination of treatment emergence will be assumed to occur after treatment unless partial date documents the AE as happening prior to treatment
- Missing AE start times for the determination of treatment assignment will be assumed to occur after treatment on the recorded date one minute after dosing
- Missing AE start date will be attributed to the treatment from analysis period 1 unless the AE end date occurs before first IMP administration

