#### **5.3.5.3 Persistent or Recurrent Adverse Events**

A persistent AE is one that extends continuously, without resolution, between subject evaluation timepoints. Such events should only be recorded once on the Adverse Event Report eCRF (and Form, if appropriate). The initial severity (intensity or grade) of the event will be recorded at the time the event is first reported. If a persistent AE becomes more severe, the most extreme severity should also be recorded on the Adverse Event Report eCRF (and Form, if appropriate). If the event becomes serious, it should be reported to the Sponsor immediately (ie, no more than 24 hours after learning that the event became serious; see Section 5.4.2 for reporting instructions). If a non-serious AE becomes serious, the Investigator will complete the paper Clinical Trial Serious Adverse Event/Adverse Event of Special Interest Reporting Form and send the form to Roche drug safety. The Adverse Event Report eCRF if already completed should also be updated to serious to correspond with the Adverse Event Reporting Form information sent to drug safety.

A recurrent AE is one that resolves between subject evaluation timepoints and subsequently recurs. Each recurrence of an AE should be recorded as a separate event on the Adverse Event Report eCRF (and Form if appropriate).

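### A persistent adverse event that starts on an earlier treatment and worsens on the combination gets no count under the combination in the by-treatment TEAE tables

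*SAP*

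**What the plan says.** **Recording.** Protocol 5.3.5.3 says of adverse events that continue without resolving between evaluations: "Such events should only be recorded once on the Adverse Event Report eCRF". It keeps two grades. First, "The initial severity (intensity or grade) of the event will be recorded at the time the event is first reported". Then, "If a persistent AE becomes more severe, the most extreme severity should also be recorded on the Adverse Event Report eCRF". It asks for no date of worsening. Only an event that resolves and returns gets a new record.

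**Attribution.** SAP 17.1.1 states: "TEAEs occurring following dosing in a specific analysis period but before dosing in the next analysis period will be attributed to that specific analysis period". Two neighbouring rules show that the start of the event decides. For missing times, "Missing AE start times for the determination of treatment assignment will be assumed to occur after treatment". For treatment emergence, "AEs starting prior to medication dosing in the first period will be regarded as pre-dose AEs".

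**Tabulation.** SAP 17.1.1 plans TEAE tables by treatment, by treatment and relationship, and by treatment and severity, with this counting rule: "Subjects are counted once, per preferred term per treatment, for the most severe of multiple occurrences".

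**Periods.** SAP 9.2.2 defines three analysis periods: balovaptan alone (including the washout), itraconazole alone, and the combination. The second ends immediately before the first combination dose on Study Day 6 of Period 2, so there is no gap between them.

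**The concern.** The secondary objective is to explore safety and tolerability of balovaptan alone and with itraconazole. The protocol expects itraconazole to raise balovaptan exposure; Protocol 3.3.2.1 cites increases of at least 3.1-fold in AUC0-120h and 1.4-fold in Cmax after a single dose. An event already present that becomes worse once balovaptan is added is one plausible way for the interaction to show clinically. Protocol 1.3 makes the setting realistic: nausea, vomiting and headache are listed for itraconazole, and headache was the most frequent event in healthy subjects given balovaptan.

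The sequence is fixed and the combination is last. A rule that leaves worsening with the starting treatment can therefore only take events away from the combination. At stake is whether the by-treatment TEAE tables can show this kind of signal in the column where a reader will look for it.

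**Working it through.** The plan gives no figure to reproduce on this point, so the check applies the stated rules to example events (hypothetical) and then sizes one event.

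**Step 1: timeline.** Period 1 with its washout is Days 1 to 17. Period 2 Day 1 is then Day 18, and the first combination dose (Period 2 Day 6) is Day 17 + 6 = 23. The total is 17 + 20 = 37 days, as the protocol states.

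**Step 2: apply the rules.**

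| Event | Current rules | If worsening were also counted where it occurs |
|---|---|---|
| Starts mild on itraconazole alone (Day 21 = Period 2 Day 4), severe on Day 30 (Period 2 Day 13) | Itraconazole 1, combination 0 | Itraconazole 1 mild, combination 1 severe |
| Starts mild on balovaptan alone (Day 9), persists, severe on Day 30 | Balovaptan 1, combination 0 | Balovaptan 1 mild, combination 1 severe |
| Resolves on Day 15, recurs on Day 30 | Balovaptan 1, combination 1 (two records) | Same |
| Starts on Day 30 | Combination 1 | Same |

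Only the first two rows are affected. The second needs an event that outlasts at least 7 washout days and 5 itraconazole days (7 + 5 = 12 days) before the combination begins. The switch from itraconazole alone to the combination is therefore the main exposure.

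**Step 3: which grade is tabulated under the earlier treatment?** The record holds both grades, and the SAP does not say which feeds the severity table. Its most-severe rule is written for multiple occurrences of a term, not for two grades within one record. The worst grade is the natural reading but not a stated one. Either way the combination count is zero.

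**Step 4: size of one event.** SAP 9.1.3 uses subjects exposed within a treatment as the denominator. That is 14 if both cohorts receive 5 mg (4 + 10) or for Cohort B at 10 mg, and 4 if Cohort A is reported separately (SAP 9.1.4). Assume the subject has no other record of the same term on the combination.

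- Combination incidence: lower by 1/14 = 7.1 points; 1/12 = 8.3 if only 12 subjects reach the combination; 1/4 = 25 for n = 4.
- Combination minus starting treatment, severe events, worst grade tabulated, 14 in each column: from +7.1 to −7.1, a shift of 2/14 = 14.3 points (2/4 = 50 for n = 4).
- Same comparison, initial grade tabulated: from +7.1 to 0, a shift of 7.1 points (25 for n = 4).
- Combination minus balovaptan alone, onset on itraconazole alone: the balovaptan column does not change, so the shift is 7.1 points (25 for n = 4) whichever grade is used.

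**The case against.** The strongest reply is that the consequence is small and visible elsewhere. All adverse events are listed, with separate listings for withdrawals, deaths and serious events. An event that becomes serious must be reported within 24 hours. Laboratory, vital-sign and ECG results are summarised by treatment and scheduled time, so measured deterioration would appear under the combination. With 14 to 18 subjects the listings can be read case by case. The objective is exploratory, no hypothesis is tested, and most earlier events in healthy subjects were mild or moderate. All of this stands and limits the reach of the point. It does not put the event into the combination column, and a listing built from one record need not show when the event worsened.

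One could also argue that an event occurs in every period in which it is present or worsens. The start-based rules for missing times and for pre-dose events tell against that reading. Protocol 5.2.1 does count exacerbation as an adverse event, but it refers to 5.3.5.8, which covers conditions present at screening and does not override the single-record rule.

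A reader might infer more than the documents support:

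- That every event ongoing on the morning of Study Day 6 is misplaced. One that does not worsen is correctly placed.
- That the event will certainly appear as severe under the earlier treatment. The SAP does not say which grade is used.
- That the 14- or 50-point shift applies to balovaptan alone versus the combination in the main scenario. Onset on itraconazole alone leaves the balovaptan column unchanged.
- That the Cohort A dose decision would be misinformed. Interim reporting follows a separate plan that is not among the documents, and nothing shows that the review uses these tables.

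**Conclusion.** The gap is real. With one record per persistent event, attribution by start and no rule for worsening, an event that persists across a treatment change and worsens on the combination is absent from the combination in every by-treatment TEAE table. The direction is fixed in the combination's favour. Each such event costs the combination column 7.1 points with 14 subjects and 25 points with 4. The shift in severe events relative to the starting treatment reaches 14.3 points only if the worst grade is tabulated there and both columns have 14 subjects.

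The frequency of such events cannot be estimated from the documents. The effect is limited to descriptive tables for the secondary safety objective; the primary PK comparison and its confidence intervals are unaffected. This is worth correcting because the correction is simple, not because a main conclusion depends on it.

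**What to change.** In SAP 17.1.1, define a TEAE for a treatment as an event that starts, or increases in severity, after the first dose of that analysis period. For a persistent event that worsens after the treatment changes, tabulate the initial severity under the starting treatment and the worsened severity under the treatment being taken when it worsened. This also settles which grade feeds the severity table in these cases.

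The rule needs the date of the severity increase. The eCRF is not among the documents. If it does not already capture that date, add it, with a matching line in Protocol 5.3.5.3.

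The cost is one SAP paragraph and at most one eCRF field or completion instruction. The small downside is that some events will appear under two treatments, so a table footnote should say that by-treatment counts need not sum to the overall count.
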